Insomnia Sleep Index (ISI) is a brief self-report instrument measuring the patient's perception of both nocturnal and diurnal symptoms of insomnia during the past two weeks. The ISI comprises seven items assessing the perceived severity of difficulties initiating sleep, staying asleep, and early morning awakenings, satisfaction with current sleep pattern, interference with daily functioning, noticeability of impairment attributed to the sleep problem, and degree of distress or concern caused by the sleep problem. Each item is rated on a five-point scale and the total score indicates the severity of insomnia, with a range of possible scores from 0-28. A score higher than 14 has been indicated to be the optimal cut-off for insomnia as a disorder. The ISI has been widely used in clinical and research settings as it is brief and easy to administer, and can provide valuable information for diagnosis and treatment planning. Research has found that the ISI is sensitive in detecting changes in the patient's perception of treatment outcome, and a good degree of convergence exists between the patient and the clinician's evaluation of insomnia severity.^{13,14}

Generalized Anxiety Disorder-7 (GAD-7) is a self-reported anxiety survey utilized in primary care consisting of a 7-item anxiety scale. The instrument is well supported to use in a general population and normative data can be used to compare a subject's GAD-7 score with those determined from a general population reference group, with evidence of significant reliability and validity with congruent agreement in self-reported and interviewer-administered versions of the

scale. GAD and Depression symptoms frequently occur together, but previous studies have supported via factor analysis that this measure can detect GAD and depression as distinct dimensions.¹⁵ This measure will be used in combination with other scales to observe self-reported effects on sleep disturbances and insomnia, such as anxiety or other psychiatric disorders.

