3.2 Eligibility

Participants must meet all the following criteria on screening examination to be eligible to participate in the study:

Inclusion

1. Age \geq 18 years old
2. Has self-reported sleep disturbance
3. Insomnia Severity Index (ISI) score of \geq 15 at screening
4. Interested in understanding more about the quality of their sleep and chose to use the Sip2Sleep product for sleep
5. Willingness to do a minimum of 1 week wash out of current OTC or other products for sleep (e.g. melatonin, anticholinergics)
6. Willingness to do a minimum of 1 week wash out of any cannabis products
7. Able to receive shipment of the product at an address within the United States
8. If taking prescription hypnotics (e.g. zolpidem, zaleplon, benzodiazepines) or other class of medication for sleep, must be on a stable dose for at least 4 weeks.
9. Able to read and understand English
10. Able to use a personal smartphone
11. Has and is able to use a personal health tracking wearable device (e.g., Apple Watch, Fitbit Smartwatch, Oura Ring, etc.)
12. Able to understand and provide informed consent
13. Able to complete study assessments over 5 weeks

Exclusion

1. Research participants who have no computer, smartphone, and internet access and/or do not use a computer or smartphone
2. Concomitant Therapies:
 - a. Participants taking daily prescription medication for sleep (for example, prescription hypnotics like zolpidem, zaleplon, benzodiazepines) not on a stable dose for at least 4 weeks
 - b. Participants receiving Cognitive Behavioral Therapy for Insomnia (CBTi)

- c. Participants receiving any investigational therapies or treatments
3. Other Illnesses or Conditions: Participants who have the following co-morbidities are excluded:
- a. Confirmed diagnoses of the following sleep disorders: Narcolepsy, Restless Leg Syndrome, Circadian Rhythm Disorders
 - b. Confirmed diagnosis of Sleep Apnea that is untreated or not well controlled
 - c. Current or prior psychotic disorder
 - d. Current or prior Substance Abuse Disorder
 - e. Current or prior cardiac dysrhythmias (for example, atrial fibrillation, supraventricular tachycardia)
 - f. Currently pregnant, planning to become pregnant in the next 1 month, or breastfeeding
 - g. Allergies or adverse reactions (for example, anxiety) to Montmorency tart cherry extract and/or Venetron®

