4.0 STUDY ACTIVITY CALENDAR

Table 4.1 Study Calendar

Protocol Activities	Screening ^a	Study Duration ^b				
		Baseline	Product Use ^c	No Product Use	Product Use ^c	End of Study
Week	Up to 1 Week	Week 1	Week 2	Week 3	Week 4	
Day	Day -7 to -1	Day 1	Day 8	Day 15	Day 22	Day 29
Informed Consent	X					
Demographics	X					
Medical History	X					
Insomnia Severity Index	X	X	X	X	X	X
Eligibility	X					

Daily Objective Data Collection and Surveys ^d		X	X	X	X	X
Use of Study Product			X		X	
Generalized Anxiety Disorder-7		X	X	X	X	X
Experience Survey						X

- a. Screening to occur within 7 days prior to Baseline (Day 1)
- b. Planned duration of study is 4 weeks
- c. Participants to consume Sip2Sleep[®] product 30-60 minutes prior to lying down in bed.
- d. Participants will complete daily surveys to review objective data from wearable device collection and answer questions about their prior night’s sleep quality and level of alertness since waking.

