6.0 STUDY PROCEDURES

6.1 Study Overview

[figure not shown]

Figure 1. Study Design

Upon enrollment, the study assessments can be accessed via CHLOE mobile app available on Apple iOS and Android devices as well as any web browser. The participant's activities are as follows:

Screening (Day -7 to Day -1):

- Informed Consent
- Complete demographic and medical history data intake.
- Screening Insomnia Severity Index (ISI) assessment.
- Provide preferred shipment address for product shipment during Baseline.

Baseline Period (Day 1 to Day 7):

- Complete Insomnia Severity Index and Generalized Anxiety Disorder-7 (Day 1 only).
- Begin discontinuation of non-prescription products used for sleep.
- Begin nightly use of personal health tracking wearable device through Day 28.
- Complete daily survey to review objective data (sleep duration and sleep latency) from wearable device collection and answer questions about their prior night's sleep quality and level of alertness since waking.
- Receive shipment of study product and instructions for use.

Product Use Period (Day 8 to Day 14):

- Complete Insomnia Severity Index and Generalized Anxiety Disorder-7 (Day 8 only).
- Continue nightly use of personal health tracking wearable device through Day 28.
- Complete daily surveys to review objective data (sleep duration and sleep latency) from wearable device collection and answer questions about their prior night's sleep quality and level of alertness since waking.
- Administer nightly dose of study product 30-60 minutes prior to lying down in bed through Day 14.

No Product Use Period (Day 15 to Day 21):

- Complete Insomnia Severity Index and Generalized Anxiety Disorder-7 (Day 15 only).
- Continue nightly use of personal health tracking wearable device through Day 28.
- Complete daily surveys to review objective data (sleep duration and sleep latency) from wearable device collection and answer questions about their prior night's sleep quality and level of alertness since waking.

Product Use Period (Day 22 to Day 28):

- Complete Insomnia Severity Index and Generalized Anxiety Disorder-7 (Day 22 only).
- Continue nightly use of personal health tracking wearable device through Day 28.
- Complete daily surveys to review objective data (sleep duration and sleep latency) from wearable device collection and answer questions about their prior night's sleep quality and level of alertness since waking.

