Stratified and interaction analyses will be employed to detect between-subgroup differences in outcomes. Specifically, we will test the difference in sleep quality VAS score change between sexes and those who reported moderate-to-severe insomnia disorder on the ISI (i.e. ISI score > 14) and those who did not (i.e. ISI score ≤ 14). Testing of these differences will be conducted by including 2-way product terms between the exposure and covariate of interest in linear mixed modeling. A significant interaction will be defined by an interaction coefficient with a p-value < 0.05.

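### The ISI interaction test (> 14 versus ≤ 14) names no timepoint and reuses the eligibility cut: the lower group is empty on the screening ISI and may be very small on the Day 1 ISI

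*Combined protocol and SAP*

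**What the plan says.** Section 9.6 of the combined protocol and SAP names two subgroup comparisons for the change in sleep quality VAS: sex, and insomnia severity. The severity comparison sets "those who reported moderate-to-severe insomnia disorder on the ISI (i.e. ISI score > 14" against "those who did not (i.e. ISI score ≤ 14". It is tested by an exposure-by-covariate product term in the linear mixed model, with p < 0.05 as the criterion. No ISI visit is attached to the split.

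Section 3.2 makes the following a condition of entry: "Insomnia Severity Index (ISI) score of \geq 15 at screening". All inclusion criteria must be met.

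Section 2.2 describes the ISI as seven items with a total from 0 to 28: "Each item is rated on a five-point scale and the total score indicates the severity of insomnia". It also gives the likely source of the cut: "A score higher than 14 has been indicated to be the optimal cut-off for insomnia as a disorder".

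The calendar in section 4.0 and the overview in section 6.1 schedule the ISI at screening and on Days 1, 8, 15, 22 and 29. The first two are close together: "Screening to occur within 7 days prior to Baseline (Day 1". The Day 1 assessment belongs to the Baseline Period: "Complete Insomnia Severity Index and Generalized Anxiety Disorder-7 (Day 1 only". Section 9.4 says baseline values will be analysed, but its covariate list does not include the ISI and does not tie the split to a visit.

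**The concern.** The subgroup cut and the entry criterion fall at the same point on the same scale. A comparison of people above and below 14 needs people below, and eligibility has removed them at the only assessment it governs. Whether the test can be run, and what it means, then depends on a timepoint that the plan leaves open.

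At stake is one of the two subgroup tests that section 9.6 names. Depending on the visit, it has no second group, or has one that may be only a few people, or uses groups defined by an outcome. While the visit is open, the grouping could also be settled after the data are seen.

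**Working it through.** **1. The plan's own figure.** Section 9.1 gives 47 evaluable participants for the primary comparison. With SD 2 and correlation 0.50, the SD of the paired difference is √(2 × 2² × (1 − 0.50)) = 2. For a mean difference of 1, two-sided α 0.05 and 90% power, a paired t-test needs 44. Dividing by the Wilcoxon efficiency 3/π gives 44 / 0.955 = 46.1, so 47. A simulation of the signed-rank test at 47 gave power 0.908. The figure reproduces and does not involve the ISI split. The plan states no size or power for the interaction test.

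**2. Screening ISI.** The total sums seven five-point items, so it takes whole values from 0 to 28. Scoring 15 or more is therefore the same as scoring above 14, and the number eligible with a screening ISI of 14 or less is 0. The split is 47 versus 0 (80 versus 0 if all enrolled are used), and the product term cannot be estimated. This step needs no assumption.

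**3. Day 1 ISI.** Members of the lower group scored 15 or more at screening and 14 or less at most 7 days later. The documents do not give the size of this group, so it was simulated under assumptions:
- Screening and Day 1 scores are a stable severity plus independent errors, rounded and limited to 0–28.
- SD is 4 or 5. Section 9.1 gives an SD of 5 for detecting a 4.5-point ISI change, not as the spread of screening scores.
- Retest correlation r is 0.6 to 0.9.
- Mean before selection is 15 to 20.
- Only those with a screening score of 15 or more are kept.

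| Assumed mean, SD, r | Share with Day 1 ISI ≤ 14 | Expected number of 47 |
|---|---|---|
| 15, 5, 0.6 (largest) | 27.2% | 12.8 |
| 16, 5, 0.8 | 15.7% | 7.4 |
| 18, 5, 0.8 | 10.5% | 4.9 |
| 20, 5, 0.8 | 6.3% | 3.0 |
| 20, 4, 0.9 (smallest) | 3.0% | 1.4 |

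In the last row the chance that the group is empty is (1 − 0.030)^47 = 0.24.

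**4. Why the assumed mean starts at 15.** Section 9.1 expects about 200 screened and up to 80 enrolled, which is 80/200 = 40%. With a mean of 12, the share reaching 15 is P(Z ≥ (14.5 − 12)/4) = 0.27 for SD 4, or P(Z ≥ (14.5 − 12)/5) = 0.31 for SD 5. That is about 53 to 62 of 200 before any other criterion, short of 80. With a mean of 15 and SD 4 it is P(Z ≥ −0.125) = 0.55, which leaves room for other exclusions.

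**5. Day 8 ISI.** Section 6.1 places this assessment on the day product use begins, with dosing at night: "Administer nightly dose of study product 30-60 minutes prior to lying down in bed through Day 14". It may precede the first dose, but no completion time is given. If it does, the same selection applies as on Day 1.

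**6. Days 15, 22 and 29.** These follow at least one week of product use. The ISI is itself a secondary outcome, so grouping on them conditions on something the product may have changed.

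**7. Power of the interaction.** As a simplification of the mixed model, take two groups with SD of change 2 and a 1-point difference in change between them: SE = 2√(1/n₁ + 1/n₂), power ≈ Φ(1/SE − 1.96).
- 2 versus 45: SE 1.45, power about 10%.
- 5 versus 42: SE 0.95, about 18%.
- 12 versus 35: SE 0.67, about 32%.
- 23 versus 24: SE 0.58, about 40%.

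**The case against.** The best reply is that Day 1 is the natural reading. The protocol labels it Baseline, section 9.4 speaks of baseline values, and the cut is the cited one for insomnia as a disorder. On that reading the test can probably be run. This stands: failure to estimate is certain only for the screening ISI. It does not settle the matter, because no section ties the split to Day 1, and the lower group there may be very small.

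A reader might infer that the Day 1 split merely sorts noise and separates severity weakly. The figures do not support that. In the same simulation, over a wider grid that also includes a mean of 12, the lower group is truly milder by about 2.4 to 6.5 ISI points. The correlation of the split with true severity can be as low as 0.30, but that value occurs where the groups differ by 5.8 points, so it mainly reflects unequal group sizes.

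A reader might also take the lower group to be as large as 45% (21 of 47). That figure needs a pre-selection mean of 12, which fits the planned screening yield poorly.

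Two further objections stand in part. The simulation assumes independent errors, yet a two-week recall and a gap of at most 7 days mean the recall windows overlap by at least 14 − 7 = 7 days. And naming the visit is separable from changing the coding. Naming Day 1 alone would end the ambiguity, but it would leave a possibly tiny group.

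**Conclusion.** The point holds. The plan names no ISI timepoint, and its cut coincides with the eligibility rule. On the screening ISI the lower group has no members; this follows from the text alone. On Day 1, or on Day 8 if completed before the first dose, the term is probably estimable, but the lower group consists only of people who had scored 15 or more at screening. It is not a sampled group without moderate-to-severe insomnia. Its size of about 1 to 13 of 47 rests wholly on the assumed mean, SD, correlation and error structure. It shows that the group may be very small, not that it will be.

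It would be wrong to infer that the trial's main result is compromised: the primary analysis and its stated power do not use this split. Nor do the documents suggest that the timepoint was left open on purpose. This is a defect in one prespecified subgroup test, worth correcting because the correction is cheap.

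**What to change.** In section 9.6, name one ISI assessment made before product use (for example Day 1) and replace the 14/15 split with that score as a continuous modifier, that is, a product use × ISI term in the linear mixed model. An acceptable alternative is a cut-point inside 15 to 28 on the screening ISI, fixed before outcomes are examined. Either way, state that the inference covers only the severity range enrolled.

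The cost is one or two sentences and, for the continuous form, a linearity assumption. No new data are needed, since the ISI is already collected at screening and on Day 1. The continuous form avoids an empty or tiny group, and so does a screening cut placed near the middle of the enrolled scores. Neither removes measurement error or selection on the screening score. Neither makes the test well powered: even a near-even split gives only about 40% power for a 1-point difference, so the result should be presented as exploratory.

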9.7 Reporting Conventions

Confidence intervals and p-values will be reported at two decimal places, except when p-values are less than 0.01. P-values less than 0.01 will be reported as “< 0.01” and p-values less than 0.001 will be reported as “<0.001”.

9.8 Quality Assurance of Statistical Programing

SAS 9.4 will be used for all data analyses in a Microsoft Windows environment. All analysis code will include the author's name, date/time of writing, reference to location and nature of inputs, reference to any parent code, and detailed comments to aid in its interpretation and implementation. A secondary statistician will have access to raw data and the opportunity to independently create the main analyses. They will also be given access to the primary code to review its validity.

10.0 STUDY COMPLIANCE AND REPORTING OF DEVIATIONS FROM APPROVED PROCEDURES

Deviations

A deviation is a divergence from a specific element of a protocol and that occurred without prior IRB approval. Deviations from the approved protocol should be avoided, except when necessary to eliminate an immediate hazard to a research participant. All deviations from the protocol will be documented in study source documents and promptly reported to the IRB.

Reporting Deviations

Investigators may deviate from the protocol to eliminate immediate hazards for the protection, safety, and well-being of the study subjects without prior IRB approval. For any such deviation, the PI will notify the IRB, within 5 calendar days of its occurrence by electronic submission of a deviation notice.

11.0 STUDY OVERSIGHT, QUALITY ASSURANCE, AND DATA & SAFETY MONITORING

The study team will be familiar with anticipated and unanticipated adverse experiences. The Principal Investigator (PI) is responsible for monitoring protocol conduct and reporting to the Institutional Review Board (IRB).

12.0 ETHICAL AND REGULATORY CONSIDERATIONS

12.1 Ethical and Regulatory Standard

Ethical Standard

This study will be conducted in conformance with the principles set forth in The Belmont Report: Ethical Principles and Guidelines for the Protection of Human Subjects of Research (US National Commission for the Protection of Human Subjects of Biomedical and Behavioral Research, April 18, 1979) and the Declaration of Helsinki.

Regulatory Standard

This study is to be conducted in compliance with the IRB approved protocol and according to applicable federal, state, local and tribal laws including the following:

- US Code of Federal Regulations (CFR) governing clinical study conduct: Title 45 Part 46 – Protection of Human Subjects
- US Code of Federal Regulations relating to the Health Insurance Portability and Accountability Act of 1996: Title 45 Part 164 – Security and Privacy – Subpart E -
 - [Subpart E—Privacy of Individually Identifiable Health Information](#)
- State of California Health and Safety Code, Title 17, for research conducted in California

In addition, this study is to be conducted in compliance with applicable policies and procedures of the IRB(s) of record, applicable institutional research policies and procedures, applicable institutional clinical policies and procedures, and applicable NIH policies and procedures.

Institutional Review Board

The protocol, informed consent form(s), recruitment materials and all participant materials will be submitted to the IRB of record for review and approval. Approval of both the protocol and the consent form must be obtained before any participant is enrolled. Any amendments to the protocol or consent materials will require review and approval by the IRB before the changes are implemented in the study.

Per the federal regulations at 45 CFR 46 and State of California Health and Safety code, Title 17, must review and approve this protocol and the informed consent process and its documents prior to initiation of the study. All institutional, NIH, Federal, and State of California regulations must be fulfilled.

Any documents that the IRB may need to fulfill its responsibilities (such as protocol, protocol amendments, consent forms, information concerning participant recruitment, payment or compensation procedures, or other pertinent information) will be submitted to the IRB. The IRB's written unconditional approval of the study protocol and the informed consent document will be in the possession of the investigator before the study is initiated.

Any amendment to the protocol document and accompanying informed consent documents, as developed and provided by the PI, will require review and approval by the IRB of record before the changes are implemented in the study.

12.2 Risk Benefit Considerations

Discomforts, Risks, and Risk Mitigation

- Risks associated with the Survey: The questions used in this survey may cause temporary discomfort or distress to the participant. The survey is designed to be simple and short and is a commonly used tool in clinical studies for sleep. The participant may choose not to complete the questionnaire.
- Risks associated with Breach of Confidentiality: There is a small risk that people who are not connected with this study will learn of the participant's identity or personal information. The study staff will be GCP trained and will utilize best practices when using the data platform to ensure participant privacy protections.

Risk Level Determination

The risks to the study are minimal or unanticipated due to appropriate mitigation measures (e.g. breach of confidentiality, loss of internet access). This research meets the federally defined definition of minimal risk (45CFR 46.102(j)).

Direct benefit to research participants

Research participants have the opportunity to engage with scientists in tracking their sleep and use of the Sip2Sleep product. They will receive \$25 upon completion of study activities.

Importance of the knowledge that may reasonably be expected

This research is significant and important because it facilitates an innovative way of science where participants can be engaged to learn about their own response to their chosen intervention and the Sponsor and the public may gain knowledge about a potentially effective and safe sleep remedy.

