1.0 OBJECTIVES AND ENDPOINTS

Objectives	Endpoints/ Measurements
Primary Objective	

 To observe the effect of the Sip2Sleep® product on sleep quality for participants with self-reported sleep disturbance 	
 Change in average sleep quality score by 1 point as measured by daily 10-point visual analogue rating scale (VAS) from baseline and 1 week of no product use
Secondary Objectives	

 To assess the effect of Sip2Sleep® product on symptoms of sleep disturbance To assess the effect of Sip2Sleep® product on anxiety To assess the effect of Sip2Sleep® product on the level of alertness during the daytime 	
 Change in Insomnia Sleep Index (ISI) by 4.5 points from baseline and 1 week of no product use Change in Generalized Anxiety Disorder-7 (GAD-7) by 4.5 points from baseline and 1 week of no product use Change in average level of alertness during the daytime score by 1 point as measured by daily 10-point visual analogue rating scale (VAS) from baseline and 1 week of no product use
Exploratory Objectives	

 To observe the change in sleep duration via personal health tracking wearable device To observe the change in sleep latency via personal health 	
 Change in average nightly sleep duration as measured via personal health tracking wearable device from baseline and 1 week of no product use Change in average nightly sleep

tracking wearable device
 
3. To identify improvements for future participant-centered study designs using feedback
	
latency as measured via personal health tracking wearable device from baseline and 1 week of no product use
 
3. Assessment of patient satisfaction survey of study experience including design and use of app-based data collection tools

---	--

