12.3 Participant Characteristics

Research equity

This research has no direct exclusions related to gender. There are also no direct exclusions related to race or ethnicity.

Vulnerable Populations

Pregnancy and lactation are exclusions due to the unknown risks of product use to fetuses and newborns.

There are exclusions for individuals with specific sleep diagnoses that require medical intervention.

Volunteers with impaired decision-making capacity are excluded.

Volunteers unable to personally provide informed consent (including but not exclusive of inability to speak and read English, hearing or sight impaired, etc.) will be excluded from participating in this research.

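### The study ships a product and schedules 14 nights of use, but no described assessment solicits adverse events and no safety summary is planned

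*Combined protocol and SAP*

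**What the plan says.** **Exposure.** The baseline list in Section 6.1 includes "Receive shipment of study product and instructions for use". For the first product week it instructs participants to "Administer nightly dose of study product 30-60 minutes prior to lying down in bed through Day 14", and it gives a matching instruction for Days 22-28.

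**Data collected.** The calendar in Section 4.0 has rows for consent, demographics, medical history, ISI, eligibility, daily data and surveys, product use, GAD-7 and the Experience Survey. The daily survey covers wearable data and the participant's "sleep quality and level of alertness since waking". Section 1.0 gives the endpoint for the Experience Survey as "Assessment of patient satisfaction survey of study experience including design and use of app-based data collection tools". Section 7.1 lists the analysis data as assessments, sleep data, demographics, medications and supplements.

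**Safety.** Section 11.0 states: "The study team will be familiar with anticipated and unanticipated adverse experiences". It then makes the PI responsible for monitoring conduct and reporting to the IRB. Section 12.2 says "The risks to the study are minimal or unanticipated" and describes two risks, survey distress and breach of confidentiality. The same section says "the Sponsor and the public may gain knowledge about a potentially effective and safe sleep remedy". Section 3.2 excludes people with a previous allergy or adverse reaction to either ingredient and gives anxiety as the example. Section 12.3 excludes pregnancy and lactation "due to the unknown risks of product use to fetuses and newborns". Section 12.5 requires that a withdrawal be documented and does not ask for the reason.

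**The concern.** The study is called observational, but it supplies the product and sets the nights on which it is taken. In a remote study with no visits, what staff learn systematically about tolerability depends on what the app asks. If the app does not ask, events come to light only when a participant volunteers them, and such reports have no planned place in the data set or the report.

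Two things are at stake. First, the protocol presents knowledge about a possibly safe remedy as part of the study's importance, and nothing it plans to collect could support that word. Second, participants who leave because of an unwanted effect could not be told apart from those who tire of the app. Section 9.1 allows for up to 80 enrolled to obtain about 47 evaluable, so this group could be large.

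**Working it through.** This is mainly a check of the text, with a short calculation for scale.

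**The plan's own figure.** Section 9.1 assumes SD 2, correlation 0.50, a difference of 1 and two-sided alpha 0.05. The SD of the paired difference is √(2 × 2² × (1 − 0.5)) = 2, so the standardised effect is 1/2 = 0.5. With the Wilcoxon efficiency factor 3/π applied to a noncentral-t calculation, power is 89.95% at n = 46 and 90.6% at n = 47; simulation at n = 47 gives 90.8%. The planned 47 reproduces. It has no bearing on this point.

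**Every place where an adverse event could be collected or reported:**

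- Objectives and endpoints (1.0): no safety objective or endpoint.
- Calendar (4.0): no adverse-event row at screening, on Days 1, 8, 15, 22 or 29, or among the daily items.
- Procedures by period (6.1): none added.
- Daily survey (4.0, 6.1): wearable review, sleep quality, alertness.
- Experience Survey (1.0): satisfaction, study design and app use.
- Data elements (7.1): no event data.
- Analysis (9.6): no safety table or listing.
- Oversight (11.0): staff awareness and PI reporting, with no method of eliciting, recording or summarising events.
- Abbreviation list: AE is defined, but the abbreviation is not used in the text available.

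The count of described adverse-event assessments is 0, against 7 + 7 = 14 scheduled product nights.

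**Who would be lost.** Section 9.3 requires all study assessments, at least 60% of daily assessments in each arm, and wearable data. Someone who leaves the study cannot meet this. At the planned ceiling, 80 − 47 = 33 people, or 33/80 = 41%, could be non-evaluable with no reason recorded. The documents do not say how many of these would have taken the product.

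**What collection could show (illustration only).** If n people are dosed and no event of a kind is seen, the one-sided 95% upper bound on its rate is 1 − 0.05^(1/n):

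- n = 47: 1 − 0.05^(1/47) = 6.2%
- n = 80: 1 − 0.05^(1/80) = 3.7%

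The chance of seeing at least one event at true rate q is 1 − (1 − q)^n. The documents give no event rate, so q is assumed:

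| Assumed q | n = 47 | n = 80 |
|---|---|---|
| 1% | 38% | 55% |
| 2% | 61% | 80% |
| 5% | 91% | 98% |

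A study of this size could therefore say something about common events and little about rare ones.

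**The case against.** Several stronger readings are tempting, and the documents do not support them.

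- *A reader might infer that no adverse-event question exists.* The survey items are summarised, not reproduced, and the consent pages and the design figure are not available. What can be said is that none is described.
- *A reader might infer that staff have no way to hear of harm.* Section 11.0 gives the PI monitoring and IRB reporting duties, Section 10.0 covers deviations to remove immediate hazards, and Section 12.6 lets participants contact staff with questions, though in the context of consent. A reporting contact may also stand on pages not available here. What is missing is solicited collection.
- *A reader might infer that the protocol promises to show safety.* The sentence in Section 12.2 is hedged twice, and Section 1.0 sets no safety objective.
- *A reader might infer that anyone who stops the product becomes non-evaluable.* Section 9.3 has no adherence criterion. A participant who stops the product but keeps completing assessments and supplying wearable data stays in; only those who stop the assessments drop out.
- *A reader might take the pregnancy wording as evidence of risk to those enrolled.* It concerns fetuses and newborns, and pregnant and breastfeeding people are excluded.

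It can also be said that GAD-7 on Days 1, 8, 15, 22 and 29 and daily alertness would show worsening anxiety or drowsiness, and anxiety is the one reaction that Section 3.2 names. That is fair as far as it goes. Both are planned as efficacy outcomes, and neither would pick up any other kind of event.

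Finally, an on/off comparison of events would be weak evidence of cause. Use is open-label, and participants begin stopping other sleep products in the baseline week, so off-product symptoms may reflect that change. This limits how the table may be read. It does not argue against collecting the data.

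**Conclusion.** The point holds in this form: the plan schedules product use and describes neither solicited adverse-event collection nor a safety summary, so as written it gives no systematic tolerability data behind the word *safe* in Section 12.2. It should be fixed because the remedy is cheap and changes what the trial collects. The primary efficacy inference is untouched.

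The conclusion assumes that the survey summaries in the protocol are complete. If an undescribed item already exists, what remains is to describe it and plan its summary. The 6.2% and 3.7% bounds do not measure the defect. They are generic zero-event limits: 47 is the evaluable target and 80 the enrolment ceiling, and neither is the number who will be dosed.

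**What to change.** 1. Add one item to the existing daily app survey on all study days: any new or unwanted symptom since the last survey, yes or no, with a free-text description. Route positive answers to the PI.
2. Record the reason for every withdrawal alongside the documentation that Section 12.5 already requires.
3. Add to Section 9.6 one descriptive table of events by on- and off-product week for everyone who took at least one dose, whether evaluable or not. State beside it that open-label use and the stopping of other sleep products limit attribution. Because the survey looks back at the previous night, assign each report to the week of that night; the Day 15 survey, for example, follows the last scheduled dose of the first product week. The survey descriptions do not mention a question on whether the product was taken, so the denominator needs a record of at least the first dose.
4. If none of this is done, delete *and safe* from Section 12.2.

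The cost is one app item and one table, with slight participant burden and PI time to read positive answers. No dose, schedule or clinical rule changes.
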